11.3.2 Clinical laboratory evaluations

A central laboratory (LKF Laboratorium für Klinische Forschung GmbH, Schwentental, Germany) will be used for all safety laboratory analyses and the blood pregnancy test. Details regarding the collection, shipment of samples, reporting of results, and alerting of abnormal values will be outlined in a laboratory manual, which will be supplied to all sites. For these tests, approximately 12 mL of blood will be collected at each blood withdrawal, resulting in a total amount of 96 mL at maximum.

Urine safety analysis and urine pregnancy tests will be performed on-site. Microscopy and other appropriate tests (as needed) will be performed by the central laboratory if dipstick indicates any clinically relevant abnormality, as judged by the investigator.

All laboratory reports must be reviewed for clinical relevance, signed and dated by the investigator. A copy of all reports must be filed in patient's medical record (source document) for that visit. Urinalysis results will be recorded in patient's medical record (source document) for that visit.

Haematology: haemoglobin, haematocrit, red blood cell count (RBC), white blood cell count (WBC), differential - neutrophils, eosinophils, lymphocytes, monocytes and basophils, and platelet count

Coagulation: prothrombin time test (International normalised ratio [INR])

Biochemistry: sodium, potassium, chloride, calcium, phosphate, blood urea nitrogen, aspartate transaminase (AST), alanine transaminase (ALT), gamma-glutamyl transferase (GGT), lactate dehydrogenase (LDH), alkaline phosphatase (ALP), creatine phosphokinase (CPK), creatinine, glucose, C-reactive protein, albumin, total protein, total cholesterol, low-density lipoprotein-cholesterol, high-density lipoprotein-cholesterol, triglycerides, total bilirubin (bilirubin will be fractionated direct/indirect if elevated) and haemoglobin A1c (HbA1c)

eGFR [13] will be estimated at V1 and MPV1 based on serum creatinine value using the according CKD-EPI formula using age, sex and race as follows:

eGFR [mL/min/1.73 m²]

= 141 x Min (S_{Cr}/κ, 1)^α x Max (S_{Cr} /κ, 1)-1.209 x 0.993Age x 1.018 [if female] x 1.159 [if Black]

Using the following abbreviations / units:

S_{Cr} (standardised serum creatinine) = [mg/dL]

κ = 0.7 (females) or 0.9 (males)

α = -0.329 (females) or -0.411 (males)

Min = indicates the minimum of S_{Cr}/κ or 1

Max = indicates the maximum of S_{Cr}/κ or 1

age = [years].

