11.6.4 Visit A3/B3/C3/D3 (14 days ±2 after A1/A3/B3/C3)

The following assessments will be performed:

- Concomitant medication
- Urine pregnancy test, in women of childbearing potential
- Vital signs* (blood pressure, heart rate and tympanic body temperature; blood pressure and heart rate will be measured twice in supine position and afterwards once in standing position)
- 12-lead ECG*
- Pharmacokinetic blood withdrawal (trough level), blood sample will be taken prior to IMP intake

- Plasma D β H activity (trough level), blood sample will be taken prior to IMP intake
- Dose increase, if applicable
- Dispense IMP
- IMP accountability
- Urinalysis (dopamine and norepinephrine levels, 24-hour urine collection on the day before the visit)
- AEs
- Blood withdrawal (haematology, coagulation and biochemistry)
- Urinalysis
- Physical examination
- Number of digital scars, in scleroderma patients only

*Painful procedures should be performed only afterwards.

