**Table 1: Dosage regimen**

Daily dose	
Dose A	50 mg (half a tablet of 100 mg)
Dose B	100 mg (one tablet of 100 mg)
Dose C	150 mg (one and a half tablet of 100 mg)
Dose D	200 mg (two tablets of 100 mg)

Each next dose will start after 14 days of treatment if the previous dose was considered safe by the investigator. The up-titration is based on the following safety criteria, including but not limited to:

- Absence of symptomatic and/or clinically relevant orthostatic hypotension
- SBP > 95 mmHg or DBP > 50 mmHg
- Absence of clinically significant changes in ECG parameters (heart rate, P-R interval, QRS duration, QT and QTc interval)
- Absence of clinically significant hypersensitivity/skin allergic reactions

Patients not fulfilling the criteria for up-titration after 14 days of treatment with 50 mg zamicastat have to be withdrawn from the study.

If the patient's next dose will not be tolerated by the patient, the dose has to be down-titrated to his/her previous dose and this dose will be considered as the individual HTD, if tolerated by the patient. Treatment at the individual HTD will be for 42 days during the maintenance period.

Zamicastat has to be taken in the morning after breakfast. The patient must not take the tablet at home on visit days (A3/B3/C3/D3, MPV1, MPV2 and MPV3).

Patients taking 150 mg or 200 mg of zamicastat and who will not participate in the extension study will take 100 mg zamicastat for 14 days.

In case a patient will discontinue the study early due to the occurrence of an AE, down-titration is not mandatory, but at the investigator's discretion.

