### Dose finding period

The dose finding period will be defined as the period from the date of the first IMP intake to the day before visit D3 or the day before IMP down-titration.

The dose finding period will be split into **dose toleration periods** for each dose prescribed for that period. The period will start from the date of the IMP taken at the site at visit A1/A3/B3/C3 to the day before visit A3/B3/C3/D3 or the day before IMP down-titration.

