### 5.6.1 Adverse Events

AEs will be coded according to latest Medical Dictionary for Regulatory Activities (MedDRA®) Version 22.0.

Adverse events' data include:

- adverse event name
- start/stop dates
- ongoing
- severity (mild, moderate, severe)
- relationship (not related, unlikely, possible, probable, definite)
- action taken with study medication (dose not changed, dose reduced, drug interrupted, drug withdrawn, not applicable, unknown)
- other actions (none, medication required, tests required, withdrawn from the study, hospitalisation required or prolonged, other specification)

- outcome of event (recovered/resolved, recovering/resolving, not recovered/not resolved, recovered/resolved with sequelae, fatal, unknown)
- AE of special interest (yes or no)
- seriousness (yes or no)
- start/stop dates of drug interruption

All AEs will be presented in listings.

Summaries of adverse events will include AEs defined as **treatment-emergent adverse events (TEAEs)**, defined as AEs with the first onset or worsening after the first IMP intake and not more than 14 days after the last IMP intake.

If the start date of an AE is incomplete or missing, it will be assumed to be treatment-emergent except if the incomplete start date or the stop date indicates that the event started or ended prior to the first IMP intake or started later than 14 days after last IMP intake.

AEs will be further assigned to the following categories:

- **Serious Adverse Events (SAEs):** defined as AEs considered by the investigator as serious.
- **Adverse Event of Special Interest (AESIs):** defined as AEs assessed by the investigator as being of special interest.
- **Related TEAEs:** defined as AEs assessed as being “Possible”, “Probable” or “Definite” to IMP and include the events with missing IMP relationship assessment.
- **Unrelated TEAEs:** defined as AEs assessed as being “Not related” or “Unlikely” to be related to IMP.
- **Severe TEAEs:** defined as AEs assessed as being “Severe” in intensity and include the events with missing severity assessment.
- **TEAEs leading to down-titration:** defined as AEs where “Action taken with study medication” is indicated as “dose reduced”.
- **TEAEs leading to discontinuation:** selected as those events where “Action taken with study medication” is indicated as “drug withdrawn” or “other actions” is “discontinued from study”.
- **TEAEs leading to death:** selected as those events where outcome of event is indicated as “fatal”.

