Adverse events will be assigned to IMP dose groups based on the prescribed IMP dose at the date of AE onset. AEs with an onset date on the same day as a down-titration will be assigned to the previous dose. If the AE onset date is incomplete such that it could belong to more than one prescribed dose, the AE will be assigned to all such doses.

The following statistical output will be provided:

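### An adverse event dated on an up-titration visit (A3, B3, C3) is counted under the new, higher dose even when it was found before that dose was taken

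*SAP*

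**What the plan says.** SAP 4.3 summarises adverse events by concurrent dose, not by highest tolerated dose (HTD). SAP 5.6.1 gives the allocation rule: "Adverse events will be assigned to IMP dose groups based on the prescribed IMP dose at the date of AE onset".

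Two further sentences in SAP 5.6.1 qualify it. One handles a dose reduction: "AEs with an onset date on the same day as a down-titration will be assigned to the previous dose". The other allocates an event to several doses, but only under this condition: "If the AE onset date is incomplete such that it could belong to more than one prescribed dose". Neither covers a complete onset date that falls on the day of a dose increase.

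SAP 4.6 sets the boundary between doses: "The period will start from the date of the IMP taken at the site at visit A1/A3/B3/C3 to the day before visit A3/B3/C3/D3". The visit day therefore belongs to the dose first taken at that visit.

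On the order of events within the visit, SAP 2.5 states: "The patient must not take the tablet at home on visit days (A3/B3/C3/D3, MPV1, MPV2 and MPV3"). The schedule footnotes in both documents make the increase depend on the previous dose having been judged safe. For the trough sample, Protocol 11.6.4 specifies: "Pharmacokinetic blood withdrawal (trough level), blood sample will be taken prior to IMP intake". Protocol 12.2 counts clinically significant observations made during a visit as AEs.

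**The concern.** Safety and tolerability of the different doses is secondary objective 2, and the concurrent-dose TEAE tables are the only AE output by dose. An abnormality found before the on-site intake at A3 followed about two weeks on 50 mg with no exposure to 100 mg. Counting it under 100 mg moves it one dose level up, and the same holds at B3 and C3. The shift always runs in the same direction.

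The boundary day is one day in about 14, but it is not an ordinary day. A2, B2, C2 and D2 are telephone contacts. Scheduled laboratory tests and physical examinations in dose finding therefore fall on A3, B3, C3 and D3, where AEs are most likely to be first detected and dated. In a study of about 32 patients, a few events moved between adjacent columns could alter the apparent dose pattern.

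**Working it through.** The plan states no figure on this point, so the check is to apply its rules to the nominal schedule of a patient titrated to 200 mg.

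**Inputs.** A1 is Day 1. Each of A3, B3, C3 and D3 comes 14 days after the preceding one (A3 after A1). MPV1, MPV2 and MPV3 come 13, 27 and 41 days after D3 (Protocol schedule; SAP 4.4). Period boundaries are from SAP 4.6, the allocation rule from SAP 5.6.1, and the withheld tablet from SAP 2.5.

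**Days.** A3 = 1 + 14 = 15; B3 = 15 + 14 = 29; C3 = 29 + 14 = 43; D3 = 43 + 14 = 57. MPV1 = 57 + 13 = 70; MPV2 = 57 + 27 = 84; MPV3 = 57 + 41 = 98.

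| Onset dated on | Day | Dose under SAP 4.6 and 5.6.1 | Last dose taken before that day's intake |
|---|---|---|---|
| A3 | 15 | 100 mg | 50 mg |
| B3 | 29 | 150 mg | 100 mg |
| C3 | 43 | 200 mg | 150 mg |
| D3 | 57 | 200 mg | 200 mg |
| MPV1, MPV2, MPV3 | 70, 84, 98 | 200 mg | 200 mg |

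Three of the four visits that end a dose-finding period shift up by one level. At D3 the dose is right; only the period label changes, from dose finding to maintenance.

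**Share of days.** One day in 14 is 1/14 = 7.1%. With the ±2-day window it runs from 1/16 = 6.3% to 1/12 = 8.3%.

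**Laboratory sampling on 50 mg.** The schedule places haematology, biochemistry and coagulation at V1, A3/B3/C3/D3, MPV1, MPV3 and FU. During escalation the only one of these on 50 mg is A3. A patient later brought back to 50 mg as HTD is sampled again in maintenance.

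**Can the data separate the two cases?** The AE items listed in SAP 5.6.1 include start and stop dates but no onset time. A pre-intake finding and a reaction to the first higher dose on the same day therefore look identical to the allocation rule.

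**The case against.** The strongest reply is that few events take this route.

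- **Escalation criteria.** They require absence of clinically significant ECG changes, of symptomatic or clinically relevant orthostatic hypotension, and of clinically significant hypersensitivity or skin reactions. Clinical significance is also a main threshold for recording an abnormality as an AE (Protocol 12.1.1). Most such findings should block the increase, so no higher dose is prescribed that day. If the patient is down-titrated instead, the existing exception applies. This stands, and it limits the point mainly to laboratory and minor examination findings.
- **Other safety tables.** Laboratory, ECG and physical examination results are tabulated by visit, with clinically significant categories. A clinically significant laboratory value at A3 still appears at A3. This also stands.
- **Timing of the laboratory sample.** Protocol 11.6.4 attaches the pre-intake instruction to the trough and DβH samples, not to the safety bloods. That the safety bloods are drawn at the same time is plausible but inferred. A central laboratory "will be used for all safety laboratory analyses and the blood pregnancy test", and the documents do not say when results come back. Return after the dose decision is likewise an assumption.
- **Existing listings.** AE start dates and visit dates are both listed, so a reader could find same-day events by hand. That helps checking but does not correct the tables.

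A reader might also infer a large distortion by multiplying the affected visits by the planned 32 patients. The documents do not support that: it would count visits or blood draws, not AEs, and would assume that every patient escalates fully.

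**Conclusion.** The point holds in a limited form. The up-titration allocation is not written out, but it follows from SAP 5.6.1 read with SAP 4.6. The need for a down-titration exception suggests that the default puts a change day under the new dose. An AE found before intake and dated on A3, B3 or C3 of an escalating patient is reported one dose level too high in Tables 15.3.1.1 to 15.3.1.11.

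The size in events is unknown. No document gives an AE rate or says how onset is dated for a laboratory finding, and the number may be small. The laboratory part assumes that onset is dated to the sampling visit and that the sample precedes intake. Symptoms with an earlier recorded onset are allocated correctly, as are events that begin after the new dose is taken.

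Two stronger readings are tempting. A reader might infer that the HTD or the main tolerability conclusions are wrong; most events that determine them block escalation or fall under the down-titration exception. A reader might also infer that concomitant medications share the error. SAP 5.3 assigns a medication to every dose it was taken with, and one first started after the visit evaluation was not taken during the earlier dose period, so no error is shown there.

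**What to change.** Add a rule to SAP 5.6.1, next to the down-titration sentence, with this content: *an AE with onset on the day of an up-titration visit (A3, B3 or C3) is assigned to the previous dose if it was identified from that visit's pre-intake assessments (laboratory sample, vital signs, ECG, physical examination) or is recorded as present before the on-site intake. All other AEs with onset that day are assigned to the new dose.*

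Flag every AE dated on A3, B3 or C3 in the AE listing, and classify each as pre- or post-intake at data review. The manual step is needed because programming from dates alone cannot make the distinction. For laboratory AEs, confirm from the site record that the sample preceded intake.

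Do not simply extend the down-titration rule to all same-day events. That would move acute reactions to the first higher dose down to the lower dose, which is the opposite error.

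The cost is a short SAP addition, a listing flag, a small programming change and manual classification of what are likely to be few AEs. The SAP cites a Data Review Report already finalised on 10 March 2022, so the classification would need a documented addendum. Nothing changes in data collection, dosing or visit procedures.

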10.3 Selection of Doses in the Study

10.3.1 Selection and timing of dose for each patient

Each patient will start treatment with 50 mg zamicastat once daily (Dose A) at visit A1 and will be up-titrated step by step to the individual HTD i.e. up to 200 mg zamicastat once daily. The 100 mg tablet has to be split at the break score in two equal halves using a pill splitter.

Table 2: Dosage regimen

	Daily dose
Dose A	50 mg (half a tablet of 100 mg)
Dose B	100 mg (one tablet of 100 mg)
Dose C	150 mg (one and a half tablet of 100 mg)
Dose D	200 mg (two tablets of 100 mg)

Each next dose will start after 14 days of treatment if the previous dose was considered safe by the investigator. The up-titration is based on the following safety criteria, including but not limited to:

- Absence of symptomatic and/or clinically relevant orthostatic hypotension
- SBP > 95 mmHg or DBP > 50 mmHg
- Absence of clinically significant changes in ECG parameters (heart rate, P-R interval, QRS duration, QT and QTc interval)
- Absence of clinically significant hypersensitivity/skin allergic reactions

Patients not fulfilling the criteria for up-titration after 14 days of treatment with 50 mg zamicastat have to be withdrawn from the trial.

If the patient's next dose will not be tolerated by the patient, the dose has to be down-titrated to his/her previous dose and this dose will be considered as the individual HTD, if tolerated by the patient. Treatment at the individual HTD will be for 42 days during the maintenance period.

Zamicastat has to be taken in the morning after breakfast. The patient must not take the tablet at home on visit days (A3/B3/C3/D3, MPV1, MPV2 and MPV3).

In case a patient missed to take the dose after breakfast, (s)he should take the dose after lunch. The next dose should be taken as scheduled. If the dose was missed after lunch too, the dose for this day has to be skipped.

Patients taking 150 mg or 200 mg of zamicastat and who will not participate in the extension study will take 100 mg zamicastat for 14 days.

In case a patient will discontinue the trial early due to the occurrence of an AE, down-titration is not mandatory, but at the investigator's discretion. In case down-titration is recommended by the investigator, it should follow the same procedure as described above.

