**Table 4: Visit Names and Labels**

Period	Number	Name	Description	Label in TLFs
Screening	100	Visit 1	Screening visit. Day -12 to -5	V1
Dose finding	110	Visit A1	Day 1	A1
	120	Visit A2	8 days $\pm$ 2 after A1 (phone call)	A2
	130	Visit A3	14 days $\pm$ 2 after A1	A3
	220	Visit B2	8 days $\pm$ 2 after A3 (phone call)	B2
	230	Visit B3	14 days $\pm$ 2 after A3	B3
	320	Visit C2	8 days $\pm$ 2 after B3 (phone call)	C2
	330	Visit C3	14 days $\pm$ 2 after B3	C3
	420	Visit D2	8 days $\pm$ 2 after C3 (phone call)	D2
Maintenance	430	Visit D3	14 days $\pm$ 2 after C3	D3
	510	Visit MPV1	13 days $\pm$ 2 after D3/UV for down-titration	MPV1
	520	Visit MPV2	27 days $\pm$ 2 after D3/UV for down-titration	MPV2
Dose finding/ Maintenance	530	Visit MPV3	41 days $\pm$ 2 after D3/UV for down-titration	MPV3
	600	Early Discontinuation Visit	Within 10 days of early discontinuation	EDV
Follow-up	610	Follow-up visit [down-titration]	14 days $\pm$ 2 after MPV3/EDV (phone call)	FUV1
	620	Follow-up visit	14 days $\pm$ 2 after last IMP intake	FUV2

Unscheduled visits (UV) will be numbered and labelled based on the preceding scheduled visit, e.g. "UV A1.1" for the first unscheduled visit after the scheduled visit A1. Multiple unscheduled visits after the same scheduled visit will be numbered and labelled sequentially.

For patients attending the extension study, adverse events and concomitant medications will only be displayed up to the end date of visit MPV3.

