Concomitant medications will be assigned to IMP dose groups based on the prescribed IMP dose at the time of medication intake. If the start or end date indicates that the medication was taken concurrently with multiple doses, it will be assigned to every corresponding dose. If the start or end date is incomplete such that it could belong to more than one dose, the concomitant medication will be assigned to all such doses.

The following statistical output will be provided:

Table 15.1.8.1.1 Prior Medications – Safety Set

Table 15.1.8.1.2 Prior Medications – Full Analysis Set

Table 15.1.8.1.3 Prior Medications – Pharmacokinetic Analysis Set

Table 15.1.8.2.1 Concomitant Medications – Safety Set

Table 15.1.8.2.2 Concomitant Medications – Full Analysis Set

Table 15.1.8.2.3 Concomitant Medications – Pharmacokinetic Analysis Set

The number and percentage of patients with at least one medication within each ATC 2nd level subgroup. Substance name (or combination of substances) will be presented by HTD for prior medication, by dose for concomitant medications and overall in the corresponding analysis set. The ATC 2nd level subgroups and substance drug name within ATC 2nd level subgroup will be ordered by descending overall incidence. Medications that differ at the substance drug name level but belong to the same therapeutic category will be combined.

Table 15.1.8.3.1 Prior PAH Medications – Safety Set

Table 15.1.8.3.2 Prior PAH Medications – Full Analysis Set

Table 15.1.8.3.3 Prior PAH Medications – Pharmacokinetic Analysis Set

Table 15.1.8.4.1 Concomitant PAH Medications – Safety Set

Table 15.1.8.4.2 Concomitant PAH Medications – Full Analysis Set

Table 15.1.8.4.3 Concomitant PAH Medications – Pharmacokinetic Analysis Set

Medications for pulmonary arterial hypertension will be summarised as above.

Table 15.1.8.5.1 PAH-Approved Therapy by Visit – Safety Set

Table 15.1.8.5.2 PAH-Approved Therapy by Visit – Full Analysis Set

Table 15.1.8.5.3 PAH-Approved Therapy by Visit – Pharmacokinetic Analysis Set

The number and percentage of patients with PAH-approved monotherapy, double therapy, and triple therapy will be summarised at visits A1 and MPV3. The substance names for each therapy combination will be presented by HTD and overall in the corresponding analysis set.

Listing 16.2.1.8 Medications and Therapies – Enrolled Set

All medications, prior, concomitant and subsequent, will be listed for the patients from the enrolled set.

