#### Table 15.3.1.1 Overall Summary of TEAEs – Safety Set

An overview of TEAEs:

- TEAE
- Non-serious TEAE
- Serious TEAE
- TEAEs of special interest
- Related TEAE
- Related serious TEAE
- Mild TEAE
- Moderate TEAE
- Severe TEAE
- TEAE leading to down-titration
- TEAE leading to discontinuation
- Serious TEAE leading to discontinuation

- Related TEAE leading to discontinuation
- TEAE leading to death

will be displayed during the trial as well as the dose finding, maintenance, and down-titration periods by dose and overall for the patients in the safety set.

Table 15.3.1.2 Incidence of TEAEs – Safety Set

Table 15.3.1.3 Incidence of Serious TEAEs – Safety Set

Table 15.3.1.4 Incidence of TEAEs of Special Interest – Safety Set

Table 15.3.1.5 Incidence of Related TEAEs – Safety Set

Table 15.3.1.6 Incidence of Related Serious TEAEs – Safety Set

Table 15.3.1.7 Incidence of TEAEs Leading to Down-Titration – Safety Set

Table 15.3.1.8 Incidence of TEAEs Leading to Discontinuation – Safety Set

Table 15.3.1.9 Incidence of TEAEs Leading to Death – Safety Set

TEAEs occurring during the trial as well as the dose finding, maintenance, and down-titration periods will be summarised by concurrent dose and overall via the numbers of adverse events, as well as counts and percentages of patients having experienced adverse events during the dose finding and maintenance periods and overall. Percentages will be based on the number of patients in the safety set. Here and in the tables below the SOC and PTs within each SOC will be ordered by descending overall incidence.

In addition, the following will be provided summarised by SOC and PT for the safety set for each dose and overall:

Table 15.3.1.10 Incidence of TEAEs by Severity – Safety Set

Table 15.3.1.11 Incidence of TEAEs by Relationship to IMP – Safety Set

All adverse event data will be listed as follows:

Listing 16.2.4.1.1 Adverse Events: MedDRA Coding

Listing 16.2.4.1.2 Adverse Events: General – Enrolled Set

Listing 16.2.4.1.3 Non-Serious Adverse Events – Safety Set

Listing 16.2.4.1.4 Serious Adverse Events – Safety Set

Listing 16.2.4.1.5 TEAEs of Special Interest – Safety Set

Listing 16.2.4.1.6 AEs Leading to Discontinuation – Safety Set

Listing 16.2.4.1.7 AEs Leading to Death – Safety Set

All AEs will be displayed by patient including the PT of an AE, start and stop dates, duration and other characteristics of AEs.

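### Whole-trial ZMC 100 mg columns pool adverse events from the closing 100 mg taper with those from the 100 mg step itself: a small distortion that an existing SAP period definition can remove

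*SAP*

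**What the plan says.** **Assignment rule.** SAP 5.6.1: "Adverse events will be assigned to IMP dose groups based on the prescribed IMP dose at the date of AE onset". The one adjustment for a reduction is that "AEs with an onset date on the same day as a down-titration will be assigned to the previous dose".

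**Taper.** SAP 2.5 says that patients on 150 or 200 mg "who will not participate in the extension study will take 100 mg zamicastat for 14 days"; Protocol 10.3.1 agrees. After early discontinuation for an adverse event, tapering is left to the investigator, and Protocol 10.3.1 adds: "In case down-titration is recommended by the investigator, it should follow the same procedure as described above". SAP 4.6 defines the down-titration period accordingly: non-extension patients with study drug dispensed at MPV3 or at the early discontinuation visit.

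**Labels and window.** SAP Table 3 has one concurrent-dose label at 100 mg, ZMC 100 mg. The TEAE window runs to 14 days after the last intake, so it covers the taper. Extension patients contribute no taper time: "For patients attending the extension study, adverse events and concomitant medications will only be displayed up to the end date of visit MPV3".

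**Displays.** SAP 5.6.1 plans Tables 15.3.1.1 to 15.3.1.9 for the whole trial and separately for dose finding, maintenance and down-titration, by dose. For Tables 15.3.1.2 to 15.3.1.9, however, the clause on patient counts and percentages names only dose finding, maintenance and overall. Severity (15.3.1.10) and relationship (15.3.1.11) are introduced with "In addition, the following will be provided summarised by SOC and PT for the safety set for each dose and overall", and no period is mentioned. Percentages use the safety set as denominator.

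**The concern.** A secondary objective is the safety and tolerability of different doses, and the primary objective is to find a dosage range. A reader will therefore compare the whole-trial dose columns. The ZMC 100 mg column mixes three situations: stepping up to 100 mg, staying on 100 mg as the HTD, and coming down to 100 mg from 150 or 200 mg. An event in the third may reflect remaining exposure from the higher dose, or the reduction itself, rather than tolerability of the 100 mg step.

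No other dose column receives taper time. The patients who supply it are a selected group, namely those not continuing into the extension and some early discontinuers. With a safety-set denominator, the extra days can raise the 100 mg percentage relative to the 50 and 150 mg steps without any true dose difference. In a study of about 32 patients, a few events can change the apparent pattern.

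**Working it through.** **1. Is the taper part of planned treatment time?** The protocol synopsis gives a maximum of 124 days for patients on 200 mg. With every visit at its +2-day limit:

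- four dose-finding periods, MPV3 and taper: 4 × (14 + 2) + (41 + 2) + (14 + 2) = 123 days after A1, so day **124**, which reproduces the stated figure;
- without the taper: 4 × 16 + 43 = 107 days after A1, so day 108.

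The stated maximum is reached only if the taper counts as treatment.

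**2. One tapered patient.** Nominal time under ZMC 100 mg is 14 titration days + 14 taper days = 28, so 14/28 = 50% is taper. If the same-day rule also applies to the closing taper, which is not stated, this changes by one day.

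**3. All patients.** Let f be the fraction of patients who taper and h the fraction with HTD 100 mg. Neither is in the documents; both are assumed. Each patient is taken to contribute 14 titration days at 100 mg. HTD 100 mg patients add 42 maintenance days and tapered patients add 14.

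Taper share of 100 mg person-days = 14f / (14 + 42h + 14f)

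| | f = 0.1 | f = 0.25 | f = 0.5 |
|---|---|---|---|
| h = 0 | 1.4/15.4 = 9.1% | 3.5/17.5 = 20.0% | 7/21 = 33.3% |
| h = 0.1 | 1.4/19.6 = 7.1% | 3.5/21.7 = 16.1% | 7/25.2 = 27.8% |
| h = 0.2 | 1.4/23.8 = 5.9% | 3.5/25.9 = 13.5% | 7/29.4 = 23.8% |

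Under a flat hazard, these are also the expected shares of 100 mg events.

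**4. Effect on a percentage (illustration).** Assume a flat risk p = 0.2 of at least one TEAE per 14 days, and h = 0. The whole-trial ZMC 100 mg incidence is (1 − f)p + f[1 − (1 − p)²]:

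- f = 0.25: 0.75 × 0.20 + 0.25 × 0.36 = 24%;
- f = 0.5: 0.50 × 0.20 + 0.50 × 0.36 = 28%.

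Without the taper it is 20%. In 32 patients that is 6.4 expected patients rising to 7.7 or 9.0.

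**5. How much of the taper could be carry-over?** Protocol 6.2.2 puts steady state between Day 3 and Day 5 of once-daily dosing. If a new plateau after a reduction takes similar time, carry-over is confined to about 3/14 to 5/14 (21% to 36%) of the taper.

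**6. What can be separated in the planned tables?** The SAP 4.6 maintenance period ends on the first day of MPV3 and down-titration starts on the second, so dose-finding and maintenance displays contain no taper events. Table 15.3.1.1 gives mild, moderate, severe and related TEAEs by period, and Table 15.3.1.5 gives related TEAEs by period. Severity by system organ class and preferred term has no stated split anywhere. Event numbers can be obtained by subtracting periods. Patient counts cannot, because one patient may have events in several periods.

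**The case against.** The strongest reply is that most of the separation already exists. In Tables 15.3.1.1 to 15.3.1.9, the 100 mg cell of the down-titration block is in effect the missing label. All adverse events are also listed by patient with start dates. That stands, and it confines the problem to the whole-trial columns and the last two tables. The table shells in SAP Appendix 1 are not among the documents reviewed, so one can say only that no split is stated.

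Other replies also stand:

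- **Unequal time is built in.** A patient on 200 mg spends 56 days there against 14 at a step. On the assumptions of the illustration, with all patients completing 200 mg, that column would show 1 − 0.8⁴ = 59%. The taper's move from 20% to 24–28% is smaller.
- **Most taper days are probably at 100 mg exposure**, given the time to steady state, so the dose label is literally right for them.
- **Reductions during dose finding** also place events that follow a higher dose in a lower column. The proposed change does not address those.

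Two stronger readings are tempting. A reader might infer that the effect arises only in patients who decline the extension. Protocol 10.3.1 and SAP 4.6 also allow tapering after early discontinuation. A reader might also infer that the figures show events charged to the wrong dose, which no adjustment for time could repair. They do not: they rest on a flat hazard and measure extra time at 100 mg, which a person-time rate would remove under that same assumption. True misattribution would survive such a rate, but nothing in the documents allows it to be sized.

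**Conclusion.** The concern holds in limited form. Taper-onset TEAEs enter the whole-trial ZMC 100 mg columns of Tables 15.3.1.1 to 15.3.1.9. They also enter Tables 15.3.1.10 and 15.3.1.11, where no period split is stated. The real size is unknown because the documents give neither extension uptake nor the HTD distribution, and the ranges shown depend on the assumed f and h.

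The documents do not support the conclusion that the comparison of doses as a whole is unsound. The period displays allow a clean reading for dose finding and maintenance. The study is descriptive, and no sample size, alpha or power is affected. This is a small distortion of one pooled column, worth removing because doing so is cheap.

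**What to change.** 1. In SAP 4.3 (Table 3) and 5.6.1, use the SAP 4.6 down-titration period to define a separate label, ZMC 100 mg (down-titration). Apply it to taper-onset TEAEs in the whole-trial by-dose columns and in Tables 15.3.1.10 and 15.3.1.11. Adding the period split to those two tables would serve equally well there.
2. Keep these events in Overall, so that none is lost.
3. State in SAP 5.6.1 that Tables 15.3.1.2 to 15.3.1.9 give patient counts and percentages for the down-titration period too.
4. Optional: treat the by-dose concomitant-medication tables likewise. SAP 5.3 uses a similar rule, "Concomitant medications will be assigned to IMP dose groups based on the prescribed IMP dose at the time of medication intake", but a medication counts under every dose it overlaps. Ongoing therapy is therefore already in the 100 mg column, and only medication newly started in the taper would move.

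The cost is SAP wording, a change to the table shells and one programming flag from a period already defined. No new data are needed. The drawback is a sparse extra column.
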